- a. At the 3-month post study intake survey, we expect that CSOs assigned to CRAFT-C will report a greater proportion of IPs entering treatment as compared to the CRAFT-A and PEER groups, and the CRAFT-A group will report a greater proportion of IPs entering treatment as compared to the PEER group.

Secondary Hypotheses:

- b. At the 2-month and 3-month post study intake survey, CSOs in all three groups will report that their relationship happiness has improved relative to baseline as measured by the Relationship Happiness Scale (RHS).
- c. At the 2-month and 3-month post study intake survey, CSOs in all three groups will self-report that their own anxiety, depression, anger and physical illness has improved relative to baseline as measured by the POMS survey, SF12 Health Survey, and the SAS-SR work subscale.
- d. At the 2-month and 3-month post study intake survey, CSOs assigned to CRAFT-C and CRAFT-A will demonstrate higher fidelity of learning CRAFT principles as compared to the CSOs assigned to the standard condition (PEER), as measured by correct answers on the revised CRAFT knowledge test.
- e. At the 3-month post study intake survey, all three groups will report similar high satisfaction (average score above 3.5 on a 5-point scale) on Usability of the website and the CRAFT-C group will report the greatest satisfaction in the Usefulness of the website relative to the CRAFT-A and PEER groups as measured by the User Satisfaction Survey.

1.3 List the primary and secondary outcomes.

The primary outcome variable that will be measured is the CSO's reporting their IP entered treatment for their OUP or received additional treatment for their OUP.

Secondary outcome variables that will be measured include CSO and IP relationship happiness; CSO's physical and mental health status; CRAFT knowledge of CSOs; and CSO's satisfaction with website content and delivery.

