4.	Missed work	SAS-SR – Work, Housekeeping, School sections (sections: A, B, C) only.	Baseline, 8-Week &12-Week Post Enrollment
5.	Depression, Anxiety, Anger	POMS	Baseline, 8-Week &12-Week Post Enrollment
	Physical illness	SF12 Health Survey	Baseline, 8-Week &12-Week Post Enrollment
6.	Learning CRAFT	Revised Family Training Survey	Baseline, 8-Week &12-Week Post Enrollment
7.	User satisfaction	Usefulness and Usability Survey	8-Week and 12-Week Post Enrollment only

Revised measures have been adapted specifically for CSOs with IPs with an OUP, as appropriate. In addition, we added questions specific to the impact of COVID-19 on the CSO, the CSO's contact with the IP, and IP's ability to access treatment and to receive quality treatment due to COVID-19 restrictions. The IP's treatment entry is the study's primary outcome and we need to understand the impact of COVID-19 on our participants' IPs gaining and receiving treatment to assess the study's impact on a primary outcome.

Participants may be contacted through email, text, calls, letters, and social media direct messaging. In addition, we will ask participants to give us the names and contact information for two people who can reach them if all other contact methods fail. Participants will be able to provide the messages we can send and/or leave, as well as any instructions they wish for us to follow when attempting to contact them or the contacts they shared with us.

Data collected from other sources (identify each source; e.g., health care provider, parent, public records):

N/A. We will only collect information directly from the study participants. We will not collect information from the CSO's IP.

4.3 Describe pre-defined criteria for removing participants from the study and the procedures for informing participants of their removal from the study. Include information on the handling of their data and measures to ensure individuals' safety and privacy after ceasing research activities.

Participants may be removed from the study for the following reasons:

- a. They engage in hostile behavior with other participants during online interactions
- b. They break the confidentiality and share personal information of other participants

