Yes. CSOs who become pregnant during the study will be able to continue. The proposed study is a behavioral health intervention and is conducted online. We do not expect pregnant participants to require additional accommodations because they can participate via a smartphone or computer at any location.

9.6 Describe the potential direct benefits to individual participants or to others as a result of study participation. Indicate if there may not be any direct benefits to participants or to others.

Participants may not receive direct benefits from this study; however, the study uses teaching approaches when delivered face-to-face have been shown to help people interact with their loved ones using healthier strategies. In addition, participants may feel more supported by engaging with other CSOs or by interacting with their coach, depending on their assigned group. Current WTV members have reported increased level of happiness, support, and healthy behaviors.

9.7 Define reportable and non-reportable Adverse Events (AEs).

Reportable AEs:

Will be defined as: significant discomfort from answering research questions or participating in the treatment intervention such that the participant decides to stop their participation, reports of new diagnoses of

depression, anxiety, or panic attacks. In addition, we will document reports from the CSO of domestic or intimate partner violence that may occur during their time in the study. We plan to collect reportable AEs that occur for the participant.

Non-reportable AEs:

Clinically insignificant events are not considered AE's. Examples of clinically insignificant events include mild viral illness (e.g., colds, flu, and runny nose), common headaches, minor scratches, and mild symptoms or problems associated with medical conditions or accidents not related to drug use (e.g., back pain). As per the definition of AEs, only significant worsening of psychiatric problems or new problems will be reported as AEs. We will monitor attrition rates but drop out from the study will not be reported as an AE.

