Reportable SAEs: will be defined as death; a life-threatening event such as suicidal attempt, or inpatient hospitalization (including psychiatric hospitalizations) due to suicidal behavior, or psychiatric distress; or substance use overdose; or an event that extends an existing hospitalization as defined above. Although we do not believe the study procedures or intervention places participants at increased risk for clinical worsening, we will review and report events of clinical worsening that leads to a psychiatric hospitalization of the participant. We plan to collect reportable SAEs that occur from the participant. These events are not anticipated to occur on a regular basis, if at all, for participants.

9.8 Define reportable Serious Adverse Events (SAEs). Choose one or both as applicable to your study.

Any adverse event that:

1. Results in death;
2. Is life-threatening (places the subject at immediate risk of death from the event as it occurred);
3. Results in inpatient hospitalization or prolongation of existing hospitalization;
4. Results in a persistent or significant disability/incapacity;
5. Results in a congenital anomaly/birth defect; or
6. Based upon appropriate medical judgment, may jeopardize the subject's health and may require medical or surgical intervention to prevent one of the other outcomes listed above.

(OHRP Guidance on Unanticipated Problems and Adverse Events; January 15, 2007)

Other, or in addition to the above (*please describe*):

Although we do not believe the study procedures or intervention places participants at increased risk for clinical worsening, we will review and report events of clinical worsening that leads to a psychiatric hospitalization. We plan to collect reportable SAEs that occur for the CSO from the CSO participants. These events are not anticipated to occur on a regular basis, if at all.

9.9 Describe plans to identify, monitor, manage, and report AEs and SAEs. Include information on the method and frequency of collecting AE and SAE information (e.g., weekly through telephone calls, monthly at study visits, every time the subject comes to the clinical setting), the individuals responsible for collecting this information (e.g., research assistants, case managers, counselors), and the start and end of collection (e.g., from the participant's first exposure to the intervention to their last study visit).

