All WTV and PHMC staff who interact with participants or monitor online conversations will be trained on the definitions of reportable and non-reportable AEs and SAEs and the way to complete the forms reporting them. The PI and Co-I will monitor the WTV forum and meet regularly with CRAFT counselors to track and to document any AEs and SAEs. The WTV clinical team will be interacting with participants in the CRAFT interventions on a

regular basis and will be responsible for collecting AE and SAE information shared during their interactions and reporting them to the PHMC team. In addition, the research assistant will document information related to AEs and SAEs shared when contacting participants. Also, the WTV team monitor online comments and interactions and will report any AEs or SAEs reported there to the PHMC team.

All adverse and serious adverse events occurring during the study are documented on a form, reviewed and signed by [name] and the PI, [name], and reported to the IRB. All SAEs are reported to the IRB within 48 hours of our awareness of the event (24 hours for fatal events). A summary of all SAEs and AEs that occurred during six-month pilot study will be included in any progress reports to the IRB. We will begin to collect AE and SAE information between the first intervention session and their 12-week post enrollment assessment.

9.10 Will you submit or have you submitted the protocol for additional oversight by a Data and Safety Monitoring Board (DSMB)?

Yes:

- The protocol will be submitted to PHMC's DSMB.
- PHMC's DSMB conducted the initial review on November 15, 2019.
- The protocol will be submitted to an external DSMB.
- An external DSMB or monitoring committee has reviewed the study. All reports are attached.
- No, a DSMB is not needed for this study

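### Non-serious mood harm is collected passively and by a different route in each arm, so AE counts cannot be compared between arms, and the protocol gives the POMS, which is surveyed in every arm, no harm use

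*Protocol*

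**What the plan says.** **What counts.** The reportable-AE list in Section 9.7 covers "significant discomfort from answering research questions or participating in the treatment intervention such that the participant decides to stop their participation", then "reports of new diagnoses of" depression, anxiety or panic attacks, and adds domestic or intimate partner violence. The paragraph on non-reportable events then states, as if citing that list, that "only significant worsening of psychiatric problems or new problems will be reported as AEs". Serious events are defined separately and include "a life-threatening event such as suicidal attempt, or inpatient hospitalization (including psychiatric hospitalizations) due to suicidal behavior, or psychiatric distress".

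**How events are found.** Under Section 9.9 the clinical team in contact with CRAFT participants "will be responsible for collecting AE and SAE information shared during their interactions". The research assistant records what comes up when contacting participants, and staff read forum comments. No scheduled AE question is described. Collection runs from the first intervention session to the 12-week assessment.

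**Contact by arm.** Section 4.1 gives CRAFT-A a weekly 60-minute group session and CRAFT-C a weekly 60-minute individual session, both with a coach. PEER is a forum with self-initiated participation.

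**What is measured in all arms.** The Section 4.2 table lists the POMS for "Depression, Anxiety, Anger" at baseline, 8 and 12 weeks, self-administered online, with no restriction by arm. Secondary hypothesis (c) in Section 1.2 is that CSOs in all three groups "will self-report that their own anxiety, depression, anger and physical illness has improved relative to baseline". Section 1.3 names the outcome neutrally, as physical and mental health status.

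**The concern.** Distress is a risk that Section 9.3 itself discusses, so a reader of the results will look at mood events by arm. Under Section 9.9 the number recorded depends on how often a participant talks to someone who is collecting events, and that frequency is part of the randomized treatment. A higher count in a CRAFT arm could reflect closer observation or more care-seeking prompted by a coach. A low count in PEER could reflect members who post little.

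Two further features weaken the count. Whether a diagnosis is new depends on the CSO's psychiatric history, which is not among the listed baseline measures. And the two parts of Section 9.7 disagree on whether worsening of an existing problem is reportable, while the word significant carries no threshold.

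Meanwhile a mood scale is collected by one route in all arms, and the protocol links it only to expected improvement. A mean improvement can coexist with a minority who deteriorate.

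**Working it through.** The protocol gives no event rate, power or precision figure for mood harm, so there is nothing to reproduce. The check sets the sections side by side and then sizes the problem under stated assumptions.

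**1. Routes by arm (Sections 4.1 and 9.9)**

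| | CRAFT-A and CRAFT-C | PEER |
|---|---|---|
| Weekly live contact with a person collecting AEs | yes, 60 minutes | no |
| Forum posts monitored | where participants post | yes |
| Research assistant contacts | when they occur | when they occur |
| Defined start of window | first session | none: no sessions |
| POMS survey | baseline, 8, 12 weeks | baseline, 8, 12 weeks |

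**2. Effect of uneven capture.** Planned enrolment is up to 84 (Section 3.1), so 84/3 = 28 per arm if equal. Expected count = 28 × true rate × capture. Assume 20% worsen in every arm and 80% of this is captured with a coach:
- coached arm: 28 × 0.20 × 0.80 = 4.5
- PEER, capture 40%: 28 × 0.20 × 0.40 = 2.2
- PEER, capture 20%: 28 × 0.20 × 0.20 = 1.1

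A two- to fourfold ratio appears with identical true harm.

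**3. What an empty list would show.** With 0 events in 28, the one-sided 95% upper bound is 1 − 0.05^(1/28) = 10.1%, even if capture were complete.

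**4. Mean improvement and individual worsening.** Take change scores as normal and count worsening of at least 0.5 SD of change. With mean improvement m (in SDs of change), the share is P(Z > 0.5 + m):
- m = 0.2: 24% (6.8 of 28)
- m = 0.5: 16% (4.4 of 28)
- m = 0.8: 10% (2.7 of 28)

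**5. Noise in a POMS worsening rule.** For one scale at one visit, with no true change and a threshold of 1 baseline SD, the flag rate is P(Z > 1/√(2(1 − r))), where r is the assumed test-retest correlation:
- r = 0.8: 5.7%
- r = 0.7: 9.8%
- r = 0.5: 15.9%

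A rule that flags depression or anxiety, at 8 or 12 weeks, has four chances to fire. Simulated with independent visit errors and errors across scales either independent or correlated 0.5-0.7, it flags about 15-19% at r = 0.8 and 36-44% at r = 0.5. That is a reason to name one scale and one visit.

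**6. Precision.** The 95% half-width of a difference between two arms of 28 is 1.96 × √(2p(1 − p)/28):
- p = 0.06: 12 points
- p = 0.15: 19 points

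**7. The 8-week survey.** Section 6.2 makes it depend on a consent addendum. Coaches raise the addendum in session for Programs A and B, while Program C gets a forum post; those who decline or do not respond are not sent the survey. Missing 8-week scores may therefore differ by arm. The 12-week survey does not depend on the addendum.

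**The case against.** **The protocol has no analysis section, and a table of deterioration by arm is ordinary SAP content.** This stands. A reader might infer that deterioration on the POMS will never be tabulated. The document does not say so: it is silent, and Section 1.3 words the outcome without direction. What remains is that the protocol names no harm use for the POMS. How AEs are collected is different in kind: Section 9.9 fixes it, and an SAP cannot recover events that nobody asked about.

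**Mood harm has more routes than stopping or a new diagnosis.** This also stands. Section 9.7 counts significant worsening, and suicide attempt and psychiatric hospitalization are SAEs. A reader might infer that the trial would most likely record no mood events. If 15% worsen and only 10% of these are diagnosed and mention it, the chance of none in 28 is (1 − 0.015)^28 = 66%. That models the diagnosis route alone. If all routes together capture 30% or 50%, it falls to (1 − 0.045)^28 = 28% or (1 − 0.075)^28 = 11%. None of these capture rates is in the protocol, so no such figure should carry the point.

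**Section 9.7 serves IRB reporting in a pilot and promises no comparison by arm; Section 9.3 reports no significant emotional upset in the team's earlier studies.** Both are fair, and they limit the urgency. They do not make an arm-dependent count interpretable if it is reported.

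**Staff are trained on the definitions and each event form is reviewed and signed.** This improves the handling of events that reach the form. It supplies no baseline history and does not equalize who is heard. The measures list is a brief description and the full survey is not shown, so the statement is limited to the listed measures.

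**Conclusion.** The point holds for non-serious mood harm. Collection is passive, its intensity differs by arm through the treatment itself, and its start is undefined for PEER. AE counts therefore do not support a comparison between arms. This follows from Sections 4.1 and 9.9 without any assumption; only the size does not. A two- to fourfold spurious ratio arises under the assumed capture rates of 80% against 40% or 20%.

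A POMS table would replace an arm-dependent method with a common one, but it is no proof of safety. Noise alone flags about 6-16% per scale per visit, expected equally in every arm, and a between-arm difference carries a half-width of about 12 to 19 points at flag rates of 6-15%. These figures assume 28 analysed per arm, r between 0.8 and 0.5, and normal scores; missing surveys would widen the interval. The change is a cheap improvement that should be made.

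**What to change.** 1. **Ask the same question in every arm (Sections 4.2 and 9.9).** Add one short item to the baseline, 8-week and 12-week surveys on diagnosis, or significant worsening, of depression, anxiety or panic. New can then be derived from study data. Start AE collection at randomization in all three arms.
2. **Name a descriptive harm use for the POMS.** Report by arm, with 95% intervals, the number and share of CSOs whose depression score worsened from baseline by at least 1 pooled baseline SD at 12 weeks. Show anxiety separately. Show any 8-week result separately too, with the number who completed that survey in each arm.
3. **Reconcile Section 9.7.** The reportable list, which names new diagnoses, and the later sentence on significant worsening must state the same definition and say how significant is judged.

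**Cost.** One survey item, one table and a wording change. Participants who have already completed baseline can give their history only by recall at a later survey. Some flagged worsening will be noise, so the table should be labelled descriptive and not read as individual diagnoses or as a firm safety conclusion by arm.

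### Section 9.9 opens adverse event collection at the first intervention session, after events that 9.7 and 9.9 themselves cover, and every stated capture route is passive

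*Protocol*

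**What the plan says.** Section 9.9 gives the collection period as: "We will begin to collect AE and SAE information between the first intervention session and their 12-week post enrollment assessment". The form's prompt for that section offers, as an example of a start and end, the participant's "first exposure to the intervention to their last study visit".

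Two other statements define the scope more widely. Section 9.9 also says: "All adverse and serious adverse events occurring during the study are documented on a form". Section 9.7 lists as a reportable event "significant discomfort from answering research questions or participating in the treatment intervention such that the participant decides to stop their participation", and it undertakes to document partner violence reported by the participant at any time while in the study.

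Section 9.9 names three capture routes:
- The clinical team working with the CRAFT arms "will be responsible for collecting AE and SAE information shared during their interactions".
- On the research side, "the research assistant will document information related to AEs and SAEs shared when contacting participants".
- For online activity, "the WTV team monitor online comments and interactions and will report any AEs or SAEs reported there to the PHMC team".

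Section 3.2 fixes the order of events. The participant passes the consent quiz on the confirmation call and is then considered enrolled. The HIPAA form, locator form and baseline survey follow, with one week allowed to finish. Randomization comes only after the baseline survey, and program notification after that. Program A participants may also wait for a group to form.

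**The concern.** A collection window should open no later than the first event that the protocol calls reportable. Here it opens later. The baseline survey is the first set of research questions after the confirmation call, and discomfort with research questions is one of the few reportable events that 9.7 spells out. Someone who stops because of that survey meets the definition, yet the window has not opened.

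The loss would be hard to see afterwards. Section 9.7 says that dropping out is not in itself an adverse event. If nobody records why a person stopped at baseline, a reportable event looks the same as an ordinary non-reportable dropout.

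The second part concerns how events come to light. The 9.9 prompt asks for the method and frequency of collection. The answer lists what participants happen to share or post, and it gives no routine question and no frequency of asking. An event that nobody volunteers can go unrecorded in any arm, and PEER participants have the fewest scheduled occasions to mention one.

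**Working it through.** The plan gives no figure to reproduce, so the check sets the sections side by side.

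**Step 1: chronology (sections 3.2 and 4.1).** The order in every arm is: consent form, confirmation call with quiz, HIPAA authorization, locator form, baseline survey, randomization, notification of program, first intervention contact. The 8-week and 12-week surveys follow.

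**Step 2: compare each covered event with the window.**
- Discomfort from the baseline survey that leads to stopping: covered by 9.7, before randomization, so before any session. Outside the window.
- Discomfort from the 8-week survey: covered by 9.7 and, for a participant who has begun the program by then, inside the window.
- Partner violence between the confirmation call and the first session: covered by 9.7, which refers to the participant's time in the study. Outside the window.
- Any other reportable event in that interval: covered by the statement in 9.9 about all events in the study. Outside the window.

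**Step 3: does the result depend on when enrollment occurs?** Section 3.2 places it at the confirmation call, 6.2 calls HIPAA authorization the final enrollment step, and 4.1 counts the baseline survey as part of enrollment. The choice affects whether a person stopping at baseline is described as already enrolled. It does not affect the order: on all three readings the baseline survey comes before randomization and before any session. The 9.7 item on research questions is not tied to enrollment.

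**Step 4: the start point in PEER.** Sections 4.1 and 6.2 use the word session for scheduled coach meetings in Programs A and B. Program C is a forum that members use when they choose, although 4.1 also mentions weekly peer-led discussions. Section 9.9 does not say which forum event counts as the first session. Candidate dates exist: program notification (3.2), or first forum access in line with the prompt's example.

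**Step 5: capture.** Each of the three routes in 9.9 starts with the participant sharing or posting something. The 4.2 table lists mood (POMS), health (SF12), social adjustment, relationship, knowledge, treatment entry and satisfaction measures, and no adverse event measure. The CRAFT programs run weekly for 12 weeks with a coach session each week, so there are 12 scheduled coach contacts per participant in those arms and none in PEER.

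**Step 6: size.** The interval from enrollment to first session is not fixed. The one-week allowance covers only the enrollment steps, and the wait for a Program A group depends on a recruitment rate that the protocol does not give. No event rates are given either. The number of events missed cannot be computed.

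**The case against.** The best defense is that the window sentence is loosely worded and the broader one in the same section governs. All staff who deal with participants are trained on the event definitions, the research assistant records what is shared on any contact in any arm, and section 3.2 already has staff contacting people who do not finish the baseline survey. A baseline event that is disclosed would probably be recorded. This stands as far as it goes: a reader might infer that staff will discard such events, and the text does not show that. It shows two rules that give different answers, and an outreach call whose stated purpose is to encourage completion, not to ask why someone stopped.

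A reader might also infer that the start cannot be dated at all in PEER. That is too strong, since notification or first forum access would serve; the protocol has simply not chosen. Nor is a start after enrollment wrong in itself, because the form's own example begins at first exposure. The fault lies in the conflict with 9.7 and the rest of 9.9.

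On capture, spontaneous reporting contradicts nothing in the document. The study is described as minimal risk, and forum monitoring and the research assistant route do reach PEER. The count of coach sessions therefore understates PEER's opportunities to report. The questionnaires themselves are not shown, so the absence of event items is read from the table of measures only. These points lower the weight of the second part. They do not supply the method and frequency that the prompt requests.

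Two further inferences are not supported. Unequal coach contact might suggest a biased safety comparison, but no between-arm comparison of adverse events is stated. It might also seem that the window closes before the last CRAFT session. The document closes it at the 12-week assessment, whose actual date for a given participant is not fixed, so this cannot be established.

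**Conclusion.** The concern holds, as a minor one. The stated window is inconsistent with 9.7 and with the scope sentence in 9.9. Taken literally, it leaves out discomfort caused by the baseline survey and every event before the first session, in all three arms. The start is undefined, though definable, for PEER. The stated capture routes are wholly passive, with scheduled coach contact only in the CRAFT arms.

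What is at stake is complete safety capture in a study described as minimal risk, not the validity of a planned test. The conclusion on the window rests on the order of events in 3.2 and on no assumption about recruitment or event rates. The conclusion on capture assumes that the 4.2 table lists all the survey content that bears on adverse events.

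**What to change.** 1. In 9.9, state one start point for all three arms: enrollment at the confirmation call as in 3.2, or another dated point no later than the baseline survey. Keep the end at the 12-week assessment.
2. Reconcile to that window the 9.7 wording on time in the study and the 9.9 sentence on all events in the study.
3. At the existing outreach to people who do not complete the baseline survey, record whether discomfort was the reason for stopping.
4. Add the same few adverse event and serious adverse event items, covering the events listed in 9.7, to the existing 8- and 12-week surveys in every arm. The 12-week items should cover the whole period from the start point, because section 6.2 lets participants decline the 8-week survey.

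The cost is slightly longer surveys and an IRB amendment. Staff would also have to read survey responses promptly, because awareness of a serious event starts the 48-hour IRB reporting clock in 9.9 (24 hours if fatal).
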